In pursuit of our long-term goal, our team has recently developed a framework for prosthetic socket design and fabrication [26] that involves: 1) non-invasive imaging to record patient geometry, 2) indentation to assess tissue mechanical properties, 3) data-driven and automated creation of patient-specific designs, 4) patient-specific finite element analysis (FEA) and design evaluation, and 5) 3D printing of the end design for clinical evaluation.

II. OBJECTIVES

The overall goal of this study is to further develop and clinically assess a computational and data-driven design and manufacturing framework for mechanical interfaces that quantitatively produces transtibial prosthetic sockets in a faster and more cost-effective way than conventional processes. Traditionally, prosthetic socket production has been a craft activity, based primarily on the experience of the prosthetist. Even with advances in computer-aided design and computer-aided manufacturing (CAD/CAM), the design process remains manual. The manual nature of the process means it is non-repeatable and currently largely non-data-driven, and quantitative data is either not obtained or insufficiently employed. Furthermore, discomfort, skin problems and pressure ulcer formation remain prevalent. Through the proposed computational modeling framework, a repeatable, data-driven and patient-specific design process is made available which is based on scientific rationale.

Objective/hypothesis: The main hypothesis of this proposal is that a socket, designed using the novel computational design framework, is equivalent to, or better than, a conventional socket (designed by a prosthetist) in terms of: 1) skin contact pressures, 2) gait symmetry, 3) walking metabolic cost, 4) skin irritation levels as assessed by the dermatologist, and 5) comfort as evaluated from a questionnaire. Our hypothesis is supported by the presented pilot data which shows reduced or equivalent skin contact pressures and subject reported comfort levels for several critical anatomical regions.

Specific Aims: 1) Subject-specific biomechanical modeling for N=18 subjects, 2) Computational design and fabrication of sockets for N=18 subjects, and 3) Clinical evaluation of novel sockets for N=18 subjects.

III. STUDY POPULATION

Sample Size

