In pursuit of our long-term goal, our team has recently developed a framework for prosthetic socket design and fabrication that involves: 1) non-invasive imaging to record patient geometry, 2) indentation to assess tissue mechanical properties, 3) data-driven and automated creation of patient-specific designs, 4) patient-specific finite element analysis and design evaluation, and 5) 3D printing of the end design for clinical evaluation. This study aims to advance these approaches, and clinically assess the overall design process for N=18 transtibial amputees. Socket evaluations are conducted during standing and walking activities. For these evaluations, skin-socket interface pressures are recorded using sensors located at the skin-socket interface. During the walking evaluation, motion capture is used additionally to allow for gait analysis. Furthermore, metabolic cost is measured by indirect calorimetry using an open circuit respirometry system. These experiments are repeated for each patient's conventional socket for comparison. In addition to these quantitative evaluations, each study participant completes a socket evaluation questionnaire, and a certified dermatologist writes a report documenting skin conditions subsequent to each socket test.

The main hypothesis of this proposal is that the novel quantitative socket is equivalent to, or better than, a conventional socket in terms of: 1) skin contact pressures, 2) gait symmetry, 3) walking metabolic cost, 4) skin irritation levels as assessed by the dermatologist, and 5) comfort as evaluated from a questionnaire. Furthermore, we hypothesize that equivalence or improved socket performance can be achieved for all N=18 subjects using a single computational design framework, i.e. that we can formulate the computational design framework such that it can automatically design these sockets for all subjects without requiring algorithm adjustments from one subject to the next.

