During a second session the sockets (designed based on the image and mechanical property data) are evaluated (at the MIT Media Lab's Biomechanics department). In this session both the conventional and novel socket systems will be tested. For all subjects the order of testing (conventional or novel first) is randomized. Subjects are first asked to sit on a chair and expose their residual limb surface for force sensor placement. Recently we established a new inter-socket skin contact pressure assessment system based on flexible pressure and force sensors (A201, 111N, FlexiForce®, TekScan, Boston, MA, USA, and also F-Socket, TekScan, Boston, MA, USA). Data for an array of force sensors can be simultaneously recorded during static standing or dynamic walking exercises. Evaluating loads at select anatomical regions are of interest, these sites include: 1) the medial crest, 2) the fibular head, 3) the tibial crest, and 4) the Mid posterior wall. Sensors are secured to the skin using a thin adhesive tape (12.7 mm wide, 0.0625 mm thick, Scotch Magic®, 3M, USA) which can be removed with minimal discomfort. After sensor placement a liner is rolled over the skin and sensors. The conventional sockets are evaluated with the subject's own liner and suspension system. For evaluation with the novel socket, subjects are fitted with a custom liner (e.g. through Ottobock Healthcare GmbH) or standard commercially available liners (such as the Silosheath Double cushion 3-mm liner, Silipos Holding LLC, Niagara Falls, N.Y, USA). A commercially available sleeve is used for suspension (such as BK Suspension sleeve, Silipos Holding LLC, Niagara Falls, N.Y, USA). Next the compliant socket and rigid outer socket are donned on. For the novel sockets the outer socket is first attached to the subject's conventional foot-ankle system, and alignment is optimized by a certified prosthetists (present during all socket fitting and evaluation procedures) consulted for this study ([name], A Step Ahead Prosthetics). Once subjects have been fitted with the sockets the standing, followed by the walking exercise is conducted. For the walking exercise not only force but also metabolic cost and motion capture data are recorded. The metabolic analysis will provide an assessment of the energy expenditure while wearing either a conventional or the novel socket (discomfort may result in a less efficient or asymmetric gait causing increased energy use). For metabolic cost analysis, subjects are equipped with a breath-by-breath portable telemetric system (Model K4b², COSMED, Rome, Italy). Subjects are also equipped with 46 reflective markers (15 mm diameter) for motion capture (following the Helen Hayes marker model). For the standing evaluation subjects are asked to stand still in an upright position for 5 minutes while skin contact force (or pressure) data and resting state metabolic data is acquired.

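### Liner and suspension may change together with the socket, so the paired comparison estimates the effect of the complete socket-liner-suspension system, not of the computational socket design alone

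*Protocol*

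**What the plan says.** **The claim.** Protocol section II (Objectives) hypothesises that "a socket, designed using the novel computational design framework, is equivalent to, or better than, a conventional socket (designed by a prosthetist". Section V (Methods) repeats this in its statement of the main hypothesis and again where it introduces the experimental evaluation. The framework given the credit is listed step by step in section V: imaging, indentation, then "data-driven and automated creation of patient-specific designs, 4) patient-specific finite element analysis and design evaluation, and 5) 3D printing of the end design". Neither a liner nor a suspension system is among the steps.

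**The test.** In section V, Session 2 (phase 3), the two conditions are set up as follows.
- Conventional: "The conventional sockets are evaluated with the subject's own liner and suspension system".
- Novel: "For evaluation with the novel socket, subjects are fitted with a custom liner" "or standard commercially available liners", with one commercial product named as an example. For suspension, "A commercially available sleeve is used for suspension".
- Carried over: "For the novel sockets the outer socket is first attached to the subject's conventional foot-ankle system". No other component is stated to be common to both conditions.
- Sensors: they are taped to the skin, and "After sensor placement a liner is rolled over the skin and sensors".

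The order of the two conditions is randomized within each subject.

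**The analysis.** The SAP (Statistical analysis plan), like Protocol section III (Sample Size), uses a paired t-test at 0.05 for scalar differences between novel and conventional sockets. Neither text mentions liner or suspension.

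**The concern.** A paired comparison isolates one factor only if that factor is all that differs between the two conditions. Here up to three components can differ at once: socket, liner and suspension. Because the sensors sit beneath the liner, the liner lies between the socket wall and the point of measurement for the first-listed outcome. Skin irritation and comfort are assessed after the subject has worn the whole assembly, and gait and metabolic cost are recorded while it is worn.

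The interpretation is what is at stake. Lower or equal pressure with the novel socket could come wholly or partly from the liner or sleeve. Equally, an unfavourable liner or sleeve could hide a good socket design. In either case, a report following the present wording would credit or blame the computational framework for something the data cannot assign to it.

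**Working it through.** **Step 1. What differs between the conditions (Protocol section V, Session 2)**

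| Component | Conventional condition | Novel condition | Held constant by the plan? |
|---|---|---|---|
| Socket | Prosthetist-designed | Computationally designed, compliant socket with rigid outer socket | No (the factor of interest) |
| Liner | Subject's own | Custom or standard commercial | Not required |
| Suspension | Subject's own system | Commercial sleeve | Not required |
| Foot-ankle system | Subject's own | Same one carried over | Yes |

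**Step 2. What the paired difference estimates.** Write the mean paired difference as D = S + L + U, where S is the contribution of the socket design, L that of the change in liner and U that of the change in suspension. This is a simple additive form; any interaction makes separation harder still. The paired t-test estimates D. It estimates S only if L + U = 0, for example when liner and suspension are the same in both conditions.

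**Step 3. Do the existing safeguards remove L + U?**
- Randomized order balances period effects. L and U follow the condition whichever order is used, so they remain.
- Pairing removes differences between subjects. L and U are differences within a subject, so they remain.
- A larger N narrows the interval around D and does not move D towards S.
- The SAP has no term, restriction or sensitivity analysis for either component.

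**Step 4. The plan's own figure.** Inputs from Protocol section III: mean 97 kPa, SD 8.9 kPa, difference 10%, two-tailed alpha 0.05, power 90%.
- Difference = 0.10 × 97 = 9.7 kPa; standardized difference = 9.7 / 8.9 = 1.09.
- One-sample (paired) t-test power from the noncentral t distribution: n = 11 gives 90.2% and n = 12 gives 92.9%.

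The stated 12 is therefore reproduced to within one subject, with 8.9 kPa used as the SD of the analysed quantity. This figure neither supports nor refutes the attribution point. It supplies the scale for Step 5.

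**Step 5. Hypothetical illustration.** Assume that S = 0 and that liner and suspension together shift mean pressure by a fixed share of 97 kPa. The documents give no such shift, so the range is an assumption. The noncentrality parameter is shift × √18 / SD of differences, with 17 degrees of freedom and a two-sided critical value of 2.110. The documents do not say whether 8.9 kPa is an SD of paired differences, so two values are used: 8.9 kPa, and 8.9 × √2 = 12.6 kPa (a per-condition SD with zero correlation).

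| Assumed shift | kPa | Noncentrality, SD 8.9 | P(significant) | Noncentrality, SD 12.6 | P(significant) |
|---|---|---|---|---|---|
| 2% | 1.94 | 0.92 | 14% | 0.65 | 9% |
| 5% | 4.85 | 2.31 | 59% | 1.63 | 34% |
| 10% | 9.70 | 4.62 | 99% | 3.27 | 87% |

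The 10% row is the same size as the difference on which the sample size is based.

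**The case against.** **Comparing complete systems is a legitimate design.** Protocol section III deliberately enrols subjects whose conventional sockets are comfortable and of high quality, and testing those as they are worn is a natural comparator. Section V speaks of assessing the overall design process, and the Session 2 text calls what is tested socket systems. This stands. A reader might infer that the trial leaves its question unanswered. The documents do not support that: whether the novel system performs as well as the subject's existing one can be answered. What is lost is attribution to the socket design, and the hypothesis and the SAP comparison still name the socket.

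**The liners may not differ.** A reader might also infer that the novel-side liner will vary from subject to subject, or will always differ from the subject's own. The Protocol says neither. It permits a custom or a commercial liner, gives no rule for choosing, and does not exclude a match. A subject whose liner and suspension match in both conditions is not affected. The point is that the plan neither requires matching nor provides for recording it.

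**A custom liner might be part of the novel product.** The documents do not say whether the liner enters the computational design. If it does, it belongs to the intervention, and the hypothesis should name it. That again leads to a restated comparison.

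**The percentages say nothing about liners.** This is correct. They are ordinary paired-t power at N=18 for a shift from any cause. They assume one uniform shift with unchanged SD and use one anatomical site during standing. They do not bear on comfort, and a significant difference is not the same as meeting the hypothesis of equivalent or better.

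**Conclusion.** The point holds as a mismatch between what is compared and what is claimed. The comparison is between socket-liner-suspension systems; the hypothesis and the SAP comparison attribute the result to the computationally designed socket. This follows from the text alone and needs no assumption about the size of a liner effect. It applies to every outcome recorded or rated with the whole assembly on, and most plainly to pressure, because of where the sensors sit.

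The size of any misattribution is unknown. Under the stated hypothetical, the chance of a significant result with no socket effect runs from 9% to 99% across the shifts and SDs shown, against a nominal 5%. These figures show only that a shift of a few per cent would matter at this sample size. They are not evidence that such a shift exists. A shift in the opposite direction could mask a real socket effect.

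It should be corrected because the remedy is cheap and prevents an unsupported attribution. It does not invalidate the trial.

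**What to change.** 1. **Restate the comparison.** In Protocol sections II and V and in the SAP, define it as one between complete socket-liner-suspension systems. State that differences in pressure, comfort or other outcomes will not be attributed to the socket design alone.
2. **Record the components.** Capture liner type, liner thickness and suspension type for both conditions in each subject. Define a match in advance, and show pressure differences by whether the components matched. This should be a descriptive display only, with no test, because among 18 subjects the matched group may be small or empty.

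Whether the same liner and suspension can be used in both conditions is for the study team to decide; the documents do not allow that to be judged here.

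The cost is a narrower claim, some rewording and a few case-report fields. Neither change alters a study procedure or the sample size.

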A total of 18 subjects will be recruited for this study. The worst ratio between the mean and standard deviation for pilot contact pressure measurements for static standing was observed for the mid posterior wall, which presented with a mean of 97 kPa, and standard deviation of 8.9 kPa. If two-tailed t-test based analysis is assumed, aiming to detect at least a 10% difference with respect to this mean, with a significance level of 0.05 and a power of 90%, the theoretically required number of test subjects is 12 (power analysis based on the MATLAB *sampsizepwr* function). However, to increase the chances of significant statistics for all measures (with varying signal to noise ratios), while also anticipating potential candidate drop-out, inclusion of N=18 subjects is proposed here.

Statistical analysis of the socket clinical evaluation data will focus on the following measurements: 1) local skin contact pressures, 2) metabolic power, 3) gait parameters (symmetry indices for joint angles, positions, torques, and also ground reaction forces), and 4) the socket evaluation questionnaire. For scalar comparisons a paired t-test, with the level of significance set at 0.05, will be used to test for differences between the novel and conventional sockets. For time-series analysis of variance (ANOVA) will be used.

Inclusion and exclusion criteria

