
For the walking evaluation subjects are asked to walk at 1.4 m/s for 10 minutes on an instrumented treadmill (Bertec, Columbus, OH) while ground reaction forces are recorded, as well as 3D marker locations and the metabolic data. The marker locations are recorded at a sampling rate of 100 Hz by a 12 infrared camera motion capture system (model: T40s, Vicon Motion Systems Ltd, Oxford, UK). The locations of these markers is chosen to track joint motion.

The treadmill system used for the walking exercise is equipped with parallel bars to prevent any injury to the subject if he were to lose balance and fall. A safety harness attached to the ceiling will also be utilized if the subject makes that request. In addition, a member of the laboratory staff will also accompany the study participant to catch him/her in the event of a fall, if necessary. The participant may ask to rest or to terminate their participation in the study at any time. The socket evaluation session (walking and standing evaluations) should take no more than 4 hours to complete.

The kinematic and force plate data can be combined with inverse dynamics analysis to compute joint angles and moment profiles. Furthermore, analysis between data for the left and right limb and for the conventional and novel socket allows for comparison of symmetry measures. Symmetry indices will be derived for: 1) ankle, knee, and hip joint angle, position, torque time profiles, and 2) the vertical ground reaction forces. The metabolic measurements for standing will be

subtracted from the metabolic rate of walking trials in order to obtain the net metabolic cost of walking.

After the standing and walking exercises subjects will be requested to take off the socket and liner to expose their residual limb skin surface. The consultant dermatologist ([name]) will then inspect the skin and report on skin irritation. The dermatologist will also talk to the subjects on comfort and instruct them to fill out the developed socket evaluation questionnaire. Questions will also relate to points where contact pressure measurements will be made, thus enabling direct comparison of local comfort assessment to pressure findings. Subjects fill out their answers by drawing a line at a desired level for each of the questions. This method allows for post-processing based conversion of the input to numerical data (i.e. 0-100 %) and lacks biases associated with constrained integer number input (e.g. favoring of even/odd numbers).

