The dermatologist ([name]) involved in the study will be present during socket evaluation and will judge skin irritation as a function of socket discomfort. Actual harm is unlikely but the researchers,

dermatologist, and prosthetist are present to judge any potential harm. Feedback from the subject can be obtained promptly by researchers present, prosthetist, and/or the dermatologist present. The MIT ethical board (COUHES) will be informed of any adverse circumstances. No follow-up will be made as the procedure poses minimal risk of injury.

Informed Consent

Informed consent will be obtained. The informed consent process will be conducted prior to the initial visit by qualified and approved study personnel. Retention is based upon the decision of each participant to continue with research enrollment. Participants may discontinue at any time without consequence.

VI. DATA ANALYSIS

Personal identifiers

All data and files particular to a subject will be anonymized (subjects will be assigned a code for naming files e.g. subject1_month_day_year) and stored on password protected computers to which only the members of the research group have access.

Data storage

The data will be stored on a password protected computer server in the MIT Biomechatronics Group, Media Laboratory, [name]. Access to this server is secured by a password. Only authorized investigators associated with the study will have access to data.

Treatment of data after study completion

The data will remain in the MIT Media Laboratory secure server for future processing. Upon subject request, digital videos can be deleted from the data server once study is completed.

VII. REFERENCES

- [1] K. Ziegler-Graham, E. J. MacKenzie, P. L. Ephraim, T. G. Trivison, and R. Brookmeyer, "Estimating the Prevalence of Limb Loss in the United States: 2005 to 2050," *Arch. Phys. Med. Rehabil.*, vol. 89, no. 3, pp. 422–429, Mar. 2008.
- [2] J. E. Kurichi, W. B. Vogel, P. L. Kwong, D. Xie, B. E. Bates, and M. G. Stineman, "Factors associated with total inpatient costs and length of stay during surgical hospitalization among veterans who underwent lower extremity amputation.," *Am. J. Phys. Med. Rehabil.*, vol. 92, no. 3, pp. 203–14, Mar. 2013.
- [3] H. E. J. Meulenbelt, P. U. Dijkstra, M. F. Jonkman, and J. H. B. Geertzen, "Skin problems in lower limb amputees: a systematic review.," *Disabil. Rehabil.*, vol. 28, no. 10, pp. 603–608, May 2006.

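### The developers of the novel socket hold the data, and the text provided states neither masked data processing nor rules for reducing the recordings to outcome values; common rules and a coded socket label would close most of this gap cheaply

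*Protocol*

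**What the plan says.** **Who built the socket and who holds the data.** Protocol section I states that "our team has recently developed a framework for prosthetic socket design and fabrication". Section VI (Personal identifiers, Data storage) limits file access to the research group and authorised investigators. No independent processor or analyst is mentioned.

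**How files are labelled.** In section VI, "subjects will be assigned a code for naming files e.g. subject1_month_day_year". The stated purpose is to anonymise the subject. The example contains no socket tag, and no step to conceal the socket is described.

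**What has to be reduced.** Section V, Session 2, describes 5 minutes of standing and 10 minutes of treadmill walking with each socket. The recordings are force or pressure data at four named sites, breath-by-breath gas exchange, and 46 markers sampled at 100 Hz. Inverse dynamics, symmetry indices and subtraction of standing from walking metabolic rate are named as steps. Questionnaire answers are drawn lines, and "This method allows for post-processing based conversion of the input to numerical data (i.e. 0-100" per cent.

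**How the results are tested.** The SAP, repeating protocol section III, applies a paired t-test at 0.05 to scalars and ANOVA to time series. It does not say how a recording becomes a scalar.

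**Protection against bias.** The only measure stated in the text provided is that the order of the two sockets is randomised (section V, Session 2). Part of the SAP document was not in that text, so silence can be claimed only for what was available.

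**The concern.** Several decisions lie between a ten-minute recording and one number per subject and socket: which interval to average, which sensors or breaths to drop, which strides to keep, how to filter, and which symmetry index to compute. If these are open, and the person deciding knows the socket and belongs to the group that designed one of them, small choices can lean one way without any intent.

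Randomised order balances warm-up, fatigue and carry-over. It has no effect on decisions made afterwards at the computer. Subjects can hardly be masked to the socket they wear, so the instrumented outcomes are where the comparison could be made most objective. A paired test with 18 subjects is sensitive to a small shift that runs the same way in every pair.

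**Working it through.** **1. The plan's own figure.** The inputs come from protocol section III. The planning site is the mid posterior wall in standing, "which presented with a mean of 97 kPa, and standard deviation of 8.9 kPa". The target is a difference of one tenth of that mean, 0.10 × 97 = 9.7 kPa, tested two-sided at 0.05 and with 90% power. The plan concludes that "the theoretically required number of test subjects is 12".

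The standardised effect is 9.7 / 8.9 = 1.09. Exact power of a paired t-test (noncentral t), taking 8.9 kPa as the SD of the difference, is 0.902 at n=11, 0.929 at n=12 and 0.992 at n=18. The smallest adequate n is 11, so the stated 12 is reproduced to within one subject. Section III gives 8.9 kPa as the SD of pilot pressure measurements. Using it as the SD of paired differences is an assumption, here and below.

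**2. A systematic processing shift.** Suppose the sockets do not truly differ. If processing moves every paired difference by δ in favour of the novel socket, the t statistic with n=18 follows a noncentral t with 17 degrees of freedom and noncentrality λ = (δ / 8.9) × √18. The two-sided critical value is 2.110.

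For δ of 1%, 2% and 3% of 97 kPa (0.97, 1.94 and 2.91 kPa), the chance of a significant result favouring the novel socket rises from 0.025 to 0.064, 0.139 and 0.258.

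**3. How choosing a window could produce such a shift.** Assume two equally defensible averaging windows per trial, differing by chance with SD w. The expected lower (or higher) of two normal values lies 0.564 w from their mean. Taking the lower for the novel socket and the higher for the conventional one, in all 36 trials (18 × 2), gives δ = 2 × 0.564 × w. The documents give no value for w, so a range is shown.

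| w, % of 97 kPa | w, kPa | δ, kPa | λ | two-sided rejection rate |
|---|---|---|---|---|
| 0.5 | 0.485 | 0.55 | 0.26 | 5.7% |
| 1 | 0.97 | 1.09 | 0.52 | 7.8% |
| 2 | 1.94 | 2.19 | 1.04 | 16.7% |
| 3 | 2.91 | 3.28 | 1.57 | 31.5% |

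**4. Sensitivity.**
- If the choices achieve half the shift at w = 3% (1.64 kPa), the rate is 11.5%. At a quarter (0.82 kPa) it is 6.6%.
- Choosing windows also adds noise to the differences. Simulating this gives 28% at w = 3% and 16% at w = 2%.
- If 8.9 kPa is the SD of a single measurement and the two sockets are uncorrelated within subject, the SD of the difference is 8.9 × √2 = 12.6 kPa. At w = 3%, λ = (3.28 / 12.6) × √18 = 1.11 and the rate is about 18%. An SD of differences below 8.9 kPa would raise the rates.
- If the window is chosen without knowledge of the socket, δ is zero on average and the rate stays at 5%.

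**The case against.** **A reader might infer that the developers process the data with the socket visible and make choices trial by trial.** The documents do not say so. They do not state who extracts the values or what that person sees, and the example file name carries no socket tag. Some tag must exist, because both sockets are tested in one session and a subject-and-date code would be the same for both, but its form is not given. Nor do the documents exclude one common script for all trials. Only the absence of stated masking and of stated rules is established.

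**Reading a drawn line is close to mechanical.** This stands. The questionnaire conversion leaves little discretion, and its larger problem, that subjects know which socket they wear, is untouched by coding the sheets. The point rests on the pressure, gas-exchange and gait data.

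**Fixed rules alone would remove most of the discretion.** This also stands, which is why rules come first in the fix. Coding covers the judgements that rules leave open, such as artefacts and failed sensors.

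**Masking would leak.** Partly true. Researchers attend the sessions, walking is filmed for analysis, and liners and suspension can differ between sockets. Locking values before the key is merged still prevents choices made after the comparison has been seen.

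**Conclusion.** The gap holds for the text provided: the group that developed the novel socket holds the data, no masking of processing is stated, and no reduction rules are given for pressure traces, gas-exchange windows, or gait strides and symmetry indices.

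Its size is unknown. The range of about 6% to 31% assumes a favourable choice in every trial, an assumed window SD, and 8.9 kPa as the SD of paired differences. Within that set-up the figures are upper bounds on what choosing between two windows could do. They do not predict this trial's error rate, and nothing in the documents shows that such a bias would occur. A reader who took 31% as the expected false-positive rate would go beyond the evidence.

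This is a cheap improvement worth making before any data are processed, not a flaw that invalidates the design.

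**What to change.** Add the following to protocol section VI and to the SAP:

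1. One common set of reduction and exclusion rules for all trials and both sockets: averaging windows for pressure and gas exchange, filters, stride selection, handling of failed sensors and artefacts, and the symmetry-index formula.
2. At export, a random code replaces the socket label on every trial file and scanned questionnaire sheet. A group member who does not extract data keeps the key.
3. All scalars, exclusions and questionnaire readings are extracted and locked under code. The walking video is not used for extraction.
4. The key is merged only before the tests are run.

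**Cost.** A short script, a named key-holder and a paragraph of text, so small but not nothing. The required number of subjects is unchanged, and power at n=18 stays at 0.992 on the plan's inputs.

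**Limits.** Masking will be partial, because session staff and differing liner or suspension hardware may reveal the socket. It does not remove bias from subjects or a dermatologist who know which socket was worn; that needs separate treatment.
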